- change to a commercially available PCSK9 inhibitor antibody prior to enrolling into this study

Clinical laboratory samples must be collected and study assessments must be performed before study drug is administered.

Patients who are undergoing apheresis or plasma exchange must have their clinical laboratory samples drawn and study assessments performed before undergoing the procedure. Every effort should be made for the patient to receive study drug immediately after completion of the apheresis procedure, but patients can receive study drug 1 day before the apheresis procedure. Patients undergoing plasma exchange should receive the study drug immediately after completing the procedure. Given the impact of lipoprotein apheresis, PCSK9 inhibitors, and mipomersen on lipid parameters, it is important to match the time of the baseline activities with the timing of the week 24 activities. This would mean that the timing between the baseline sample collection relative to the most recently completed LDL apheresis procedure, administration of a PCSK9 inhibitor or mipomersen should match the timing of the week 24 sample collection relative to the most recently completed apheresis procedure, administration of a PCSK9 inhibitor or mipomersen.

Patients receiving background LMT that has been proven to reduce the risk of ASCVD (eg, statins, ezetimibe, PCSK9 inhibitor antibodies) should make their best effort to maintain a stable regimen after week 24 and for the duration of the study.

Patients receiving other LMT (eg, apheresis, lomitapide) may have that LMT adjusted after week 24, based on their LDL-C levels, CV risk factors, and judgment of the investigator.

Patients should be on a stable heart healthy diet and exercise regimen throughout the duration of the study, starting at the baseline visit and continuing through the end of the open-label treatment period.

Treatment will continue until 1 of the following occurs:

- Clinical development of evinacumab for the indication described in this study protocol is discontinued
- Clinical development of evinacumab is terminated
- Risk/benefit of evinacumab in this patient population is deemed unfavorable
- Evinacumab is approved by the regulatory authority governing the location of the study site*

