3. Fasting sample will be collected for the lipid panel: TC, calculated LDL-C, HDL-C, TG, and non-HDL-C, and the specialty lipid panel: Apo B, ratio of Apo B/Apo A-1, Lp(a), and ApoCIII.
4. Electrocardiograms should be performed before blood samples are collected at visits requiring blood draws.
5. Assessment of Tanner Stage, sex hormones, and post-baseline height only applicable to patients < 18 years old.
6. Sex hormones include luteinizing hormone, FSH, estradiol, and total testosterone
7. WOCBP only, confirm required contraception use and reminder of pregnancy reporting. For adolescent patients not of childbearing potential at Screening, confirm whether the patient is of childbearing potential at every visit. If an adolescent patient becomes of childbearing potential during the course of the study, exclusion criterion #14 applies and administer pregnancy tests administered every 4 weeks.
8. For evinacumab-naïve patients only.
9. DNA sample for HoFH genotyping should be taken only for patients who have not been enrolled in a previous evinacumab or alirocumab clinical study.
10. Carotid ultrasound imaging for adolescent patients will be performed only at sites with this capability. Every effort should be made for patients to undergo 2 carotid ultrasound imaging assessments before the first dose of study drug or as soon as possible thereafter. The assessments should be separated by at least 1 day.

8.1.3. Footnotes for Schedule of Events Table 3

1. For patients directly transitioning from a previous evinacumab study: all assessments and procedures should be performed after end of study assessments and procedures have been completed in the previous study, if applicable. Only assessments not performed at the previous end of study visit need to be performed-at the baseline visit.
2. All laboratory samples should be collected before administration of study drug.

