3. Study assessments should be performed and blood samples should be collected before study drug administration. For patients undergoing apheresis or plasma exchange: Study assessments should be performed and blood samples should be collected before the procedure. Every effort should be made for the patient to receive study drug immediately after completion of the apheresis procedure, but patients can receive study drug 1 day before the apheresis procedure. Patients undergoing plasma exchange should receive study drug after the procedure. The timing between the baseline sample collection relative to the most recently completed LDL apheresis procedure, administration of a PCSK9 inhibitor or mipomersen should match the timing of the week 24 sample collection relative to the most recently completed LDL apheresis procedure, administration of a PCSK9 inhibitor or mipomersen. Depending on the duration between the apheresis procedure and sample collection, the visit window may not apply.

4. Vital signs (temperature, sitting blood pressure, pulse, and respiration rate) should be measured before study drug administration on days when study drug is administered. On dosing days, patients should remain in the clinic for 60 minutes after the end of the IV infusion for monitoring. Pulse and blood pressure should be measured 30 and 60 minutes after the end of the IV infusion.
5. Fasting sample will be collected for the lipid panel: TC, calculated LDL-C, HDL-C, TG, and non-HDL-C, and the specialty lipid panel: Apo B, ratio of Apo B/Apo A-1, Lp(a), and ApoCIII.
6. Assessment of Tanner Stage, sex hormones, and post-baseline height only applicable to patients < 18 years old.
7. Electrocardiograms should be performed before blood samples are collected at visits requiring blood draws.
8. Sex hormones include luteinizing hormone, FSH, estradiol, and total testosterone.
9. All patients will be reminded of protocol-specified contraception use and pregnancy reporting. For adolescent patients not of childbearing potential at Screening, confirm whether the patient is of childbearing potential at every visit. If an adolescent patient becomes of childbearing potential during the course of the study, exclusion criterion #14 applies and administer pregnancy tests administered every 4 weeks.
10. The ADA sample should be drawn before study drug administration or immediately prior to the apheresis procedure, if applicable.
11. Including assay of total ANGPTL3.

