12. PK sample collected in all patients. For patients undergoing apheresis, a PK sample should be collected immediately before the apheresis procedure. For patients undergoing plasma exchange, a PK sample should be collected immediately before and after the procedure. For patients who are not undergoing apheresis, the PK sample should be drawn before the dose of study drug.
13. After the week 24 visit, visits are in a strict sequence of A through F and should occur every 4 weeks. After visit F, the sequence repeats (visits A through F) until the end of treatment visit.
14. The end of treatment visit should occur 4 weeks post the last dose. Patients who prematurely discontinue from study drug should return to the clinic within 5 days if possible for end of treatment visit assessments. At this visit, WOCBP will be provided with urine pregnancy tests with instructions to test for pregnancy at home every 4 weeks after this visit and Q4W when phone visits are scheduled (weeks 8 and 16 post last dose). Urine pregnancy testing will be done during clinic visits at week 12, week 20, and week 24. Patients who upon their study completion, may continue to receive treatment outside of the clinical trial (such as through a CUP, EAP, or ISS/IST) and thereby may forgo the 24-week follow-up period of the study. The follow-up period was intended to be an off-drug follow-up. No off-drug follow-up period is required for these patients. In this situation, the patient's EOT will be their last study visit.

15. At weeks 8 and 16 of the follow-up period all patients will be contacted by phone to query LMT compliance, to inquire about AEs or changes to concomitant medications, confirm required contraception use, and remind patients of pregnancy reporting. Women of childbearing potential will report the results of their home pregnancy test. Patients who upon their study completion, may continue to receive treatment outside of the clinical trial (such as through a CUP, EAP, or ISS/IST) and thereby may forgo the 24-week follow-up period of the study. No off-drug follow-up period is required for these patients. In this situation, the patient's EOT will be their last study visit.
16. Should be collected at the baseline visit or at any study visit for patients who have not previously been enrolled in an evinacumab or alirocumab clinical study.
17. PK sample (including ANGPTL3) only for evinacumab-naïve adolescent patients.

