5.10. Analysis of Pharmacokinetic Variables

Descriptive statistics of concentrations of total evinacumab, total ANGPTL3 will be presented. Mean concentrations of each analyte will be tabulated by visit for the study in the PK analysis set, with concentrations below the LLOQ set to zero.

Plots of the mean concentrations (linear and log scales) will be presented by nominal sampling time. Plots of the individual concentrations (linear and log scales) will be presented by actual sampling time. In the linear-scaled plots, concentrations below the LLOQ will be set to zero; in the log-scaled plots, concentrations below the LLOQ will be imputed as LLOQ/2.

Descriptive comparison of concentrations of evinacumab and total ANGPTL3 between Caucasian patients and Japanese patients may be performed if sufficient data are collected.

Concentrations of evinacumab measured before and post apheresis procedure will be summarized descriptively. Other descriptive sub-group analyses may be performed as appropriate, including concomitant medications, parent studies, previous treatment with evinacumab, adolescents, renal impairment, etc.

When appropriate, relationship between concentrations of evinacumab and LDL-C or other biomarkers may be evaluated descriptively.

The summary of pharmacokinetic variables will be provided for all patients in the study in the safety analysis set, and again for the subpopulation of adolescent patients.

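### For apheresis patients dosed the day before the procedure, Table 3 footnote 12 conflicts with the pre-dose sampling rule, and the SAP has no rule to keep a resulting post-dose PK value out of its by-visit means

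*Protocol*

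**What the plan says.** Protocol 4.3 names Ctrough as the PK variable. Protocol 8.1.3 then gives several timing rules for blood samples in Table 3.

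- Footnote 2 is attached to the laboratory block that contains the PK and ADA rows: "All laboratory samples should be collected before administration of study drug".
- Footnote 3 opens in the same sense: "Study assessments should be performed and blood samples should be collected before study drug administration". For apheresis patients it adds that sampling comes before the procedure. It asks sites to try to infuse straight after apheresis, "but patients can receive study drug 1 day before the apheresis procedure".
- Footnote 12 (PK): "For patients undergoing apheresis, a PK sample should be collected immediately before the apheresis procedure". Its next rule for patients without a procedure is: "For patients who are not undergoing apheresis, the PK sample should be drawn before the dose of study drug".
- Footnote 10 (ADA): "The ADA sample should be drawn before study drug administration or immediately prior to the apheresis procedure, if applicable".

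Protocol 5.1 repeats the pre-dose rule for clinical laboratory samples: "Clinical laboratory samples must be collected and study assessments must be performed before study drug is administered". Protocol 8.2.2.5 joins the two conditions, before dose and before apheresis, with *and/or*, so it does not settle the order.

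On the analysis side, SAP 4.10 defines the variable as concentrations at each specified time point. SAP 5.10 states: "Mean concentrations of each analyte will be tabulated by visit for the study in the PK analysis set". SAP 6.4 assigns drug concentration and ADA to study-day windows and, where several values fall in one window, takes the one nearest the target day. SAP 10.5.3 and 10.6.3 carry the same apheresis wording for PK and ADA.

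**The concern.** Footnote 12 ties the sample to the dose for one group of patients and to the procedure for the other. When the procedure follows the infusion by a day, the procedure-based rule gives a concentration soon after dosing, not one at the end of the dosing interval. Nothing in the SAP separates the two kinds of value in the by-visit tables.

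The by-visit mean concentration is the output directly exposed. The concentration/LDL-C evaluation and the assessment of antibody impact on concentrations draw on the same data. The adolescent PK summary is the most sensitive because about 14 adolescents are planned. Protocol 3.2.2 also says that a meaningful adolescent/adult difference in PK/PD would lead the sponsor to consider an amendment.

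**Working it through.** The documents give no precision target or sample-size calculation for PK, so there is no plan figure to reproduce. The check has three parts.

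**1. Can one sample satisfy every rule?**

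| Order of events | Sample drawn | Footnote 2 and opening of footnote 3 | Footnote 12 | Footnote 10 |
|---|---|---|---|---|
| Apheresis, then infusion | Before apheresis | Met | Met | Met |
| Infusion, apheresis next day | Before infusion | Met | Not met | Met |
| Infusion, apheresis next day | Just before apheresis | Not met | Met | Met |

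In the day-before order no single sample satisfies footnote 12 together with footnotes 2 and 3. Footnote 10 is satisfied either way, so for ADA it only permits the later draw.

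**2. Does the SAP keep a next-day sample?** In SAP Table 1, week 4K has target day 28K+1 and window 15+28(K-1) to 42+28(K-1). Take the infusion on the target day and the sample one day later.

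- Week 12 (K=3): target 85, window 71-98, sample day 86. Kept.
- Week 24 (K=6): target 169, window 155-182, sample day 170. Kept.
- First visit C (week 36, K=9): target 253, window 239-266, sample day 254. Kept.
- First visit F (week 48, K=12): target 337, window 323-350, sample day 338. Kept.
- Baseline: a Day 2 sample is not before first treatment and lies outside the week 4 window (15-42). The pre-dose value is lost, and no trough is contaminated.
- End of treatment and end of study: no infusion at the visit, so no effect.

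Drawing two samples would not reliably solve this. With the infusion on day 84 and apheresis on day 85, SAP 6.4 selects the day-85 value for week 12, which is the post-dose one. The selection rule uses the calendar and not time since dose.

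**3. Illustrative size.** Inputs:

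- Dose 15 mg/kg (protocol).
- Trough T = 100 mg/L. Protocol 3.2.2 says concentrations stayed above this level for about 4 weeks, so it is a lower bound.
- Distribution volume V = 0.04-0.08 L/kg, first-day loss L = 0-25% and mistimed share f. All three are assumptions with no source in the documents.

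Day-1 concentration = T + (15/V)(1-L).

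- Upper: 15/0.04 = 375; 100 + 375 = 475 mg/L; ratio 4.75.
- Lower: 15/0.08 = 187.5; 187.5 x 0.75 = 140.6; 100 + 140.6 = 240.6 mg/L; ratio 2.41.
- With an assumed trough of 200 mg/L instead: (200 + 140.6)/200 = 1.70 to (200 + 375)/200 = 2.88.

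Rise in the visit mean = f x (ratio - 1), with T = 100 mg/L:

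- f = 5%: 0.05 x 1.41 = 7% to 0.05 x 3.75 = 19%.
- f = 10%: 14% to 38%.
- f = 20%: 28% to 75%.

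One mistimed sample among 14 adolescents (f = 7.1%) adds 140.6/14 = 10 to 375/14 = 27 mg/L to that visit's mean.

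**The case against.** The strongest reply is that the protocol already requires pre-dose sampling: footnote 2, the opening of footnote 3 and protocol 5.1 all say so. Under the order footnote 3 asks sites to aim for, every footnote agrees. A post-dose PK value needs two things together: a site uses the day-before option, and it follows footnote 12 over footnotes 2 and 3. That stands, and it makes the consequence conditional. It does not remove the conflict. Footnote 12 is the specific PK instruction and confines its dose-based rule to patients without apheresis, so a site could reasonably follow it.

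A second reply is that SAP 5.10 plots individual concentrations by actual sampling time, so mistimed values would be visible. That is true, but a plot does not correct the tabulated mean. It does show that the data needed for a correction are already collected.

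Third, the stakes are limited. PK is not a listed objective, although protocol 3.2.1 says the study is intended to provide PK information. PK analysis is descriptive, the concentration/LDL-C evaluation is optional, and no primary or secondary endpoint depends on it. This stands.

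A reader might also infer that the plan will put near-peak values into trough summaries, for PK and ADA alike. The documents do not support that. The SAP has no summary labelled trough, footnote 10 offers the ADA timing only as an alternative, and no assay drug-tolerance figure is given from which to argue an effect on ADA results.

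**Conclusion.** The point holds as an unresolved conflict between footnotes with no safeguard in the analysis. For apheresis patients dosed the day before the procedure, footnote 12 cannot be reconciled with footnotes 2 and 3 or with a PK variable defined as Ctrough. If a site follows footnote 12, the SAP keeps the value in the by-visit mean at week 12, week 24 and visits C and F, and the baseline pre-dose value is lost.

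An affected sample would read about 2.4-4.8 times trough under the assumed volume and first-day loss with a 100 mg/L trough. Because 100 mg/L is a lower bound, the true ratio would be smaller if troughs are higher. The effect on any visit mean cannot be estimated from the documents: they give neither the share of patients on apheresis nor the share dosed the day before. The percentages above are illustrations and not forecasts.

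**What to change.** Protocol 8.1.3: reconcile footnotes 10 and 12 with footnotes 2 and 3, so that for apheresis patients the scheduled PK and ADA samples precede both the infusion and the procedure. This concerns sampling only and takes no position on the order of infusion and apheresis.

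SAP 5.10: classify PK samples by actual time since last dose. Exclude any sample taken after that visit's infusion from the by-visit pre-dose (Ctrough) summaries, including the adolescent summary, and list it separately. Keep it available for the planned summary of concentrations before and after apheresis. This rule also covers samples already drawn, which a footnote edit cannot.

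Cost: two footnote edits and one SAP sentence, with no extra samples and a slightly smaller n at affected visits. SAP 1 allows revision before database lock.

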8.1.4. Early Termination Visit

Patients who are withdrawn from the study will be asked to return to the clinic for 2 visits: an end of treatment/early termination visit and an end of study visit. The end of treatment/early termination visit should take place within 5 days of treatment discontinuation, if possible. A final end of study (EOS) visit should take place with assessments as specified in the EOS visit at 24 weeks after the last dose of study drug described in [Table 3](#).

Sexually active patients who discontinue the study prematurely should be reminded to maintain highly effective contraceptive measures for 24 weeks after the last dose of study drug. At the end of treatment/early termination visit, WOCBP will be provided urine pregnancy tests with instructions to test for pregnancy Q4W until the EOS visit. All patients should also be notified of Q4W follow-up phone calls to confirm contraception use, remind them of pregnancy reporting, and to obtain the results of the urine pregnancy test. Patients who upon their study completion, may continue to receive treatment outside of the clinical trial (such as through a CUP, EAP, or ISS/IST) and thereby may forgo the 24-week follow-up period of the study. No off-drug follow-up period is required for these patients. In this situation, the patient's EOT will be their last study visit.

8.1.5. Unscheduled Visits

All attempts should be made to keep patients on the study schedule. Unscheduled visits may be necessary to repeat testing following abnormal laboratory results, for follow-up of AEs, or for any other reason, as warranted.

8.2. Study Procedures

8.2.1. Procedures Performed Only at the Screening/Baseline Visit

The following procedures will be performed for the sole purpose of determining study eligibility or characterizing the baseline population: TSH, FSH, hepatitis B surface antigen, hepatitis C antibody.

8.2.2. Safety Procedures

8.2.2.1. Vital Signs

Vital signs, including temperature, sitting blood pressure and pulse and respiration rate, will be collected predose at time points according to [Table 1](#), [Table 2](#), and [Table 3](#). Post-dose blood pressure and pulse rate will be collected 30 minutes and 60 minutes after the end of the IV infusion. Blood pressure should be measured in the same arm throughout the study after the patient has been resting quietly for at least 5 minutes. Pulse rate will be measured at the time of the measurement of blood pressure.

8.2.2.2. Physical Examination

A thorough and complete physical examination including height and weight will be performed at time points according to [Table 1](#), [Table 2](#), and [Table 3](#). Care should be taken to examine and assess any abnormalities that may be present, as indicated by the patient's medical history.

8.2.2.3. Electrocardiogram

Electrocardiograms should be performed before blood is drawn during visits requiring blood draws. A standard 12-lead ECG will be performed at time points according to [Table 1](#), [Table 2](#), and [Table 3](#). Heart rate will be recorded from the ventricular rate, and the PR, QRS, RR and QT (QTcF) intervals will be recorded. The ECG strips or reports will be retained with the source.

8.2.2.4. Tanner Stages

The Tanner stages will be assessed throughout the study for all patients ≥ 12 years old and < 18 years old at specified time points shown in [Table 1](#), [Table 2](#), and [Table 3](#). If possible, for each adolescent patient, the Tanner stages assessment should be performed by the same investigator/designee trained to assess pubertal development.

8.2.2.5. Laboratory Testing

All laboratory samples will be collected at visits according to [Table 1](#), [Table 2](#), and [Table 3](#), before the dose of study drug is administered and/or before apheresis is performed, if applicable.

Detailed instructions for blood sample collection are in the laboratory manual provided to study sites and specific tests are listed below.

Blood Chemistry

Sodium	Total protein, serum	Total bilirubin
Potassium	Creatinine	Uric acid
Chloride	Blood urea nitrogen (BUN)	Creatine phosphokinase (CPK)
Carbon dioxide	Aspartate aminotransferase (AST)	
Calcium	Alanine aminotransferase (ALT)	
Glucose	Alkaline phosphatase	
Albumin	Lactate dehydrogenase (LDH)	

Hematology

Hemoglobin	Differential:
Hematocrit	Neutrophils
Red blood cells (RBCs)	Lymphocytes
White blood cells (WBCs)	Monocytes
Red cell indices	Basophils
Platelet count	Eosinophils

Urinalysis

Color	Glucose	RBC
Clarity	Blood	Hyaline and other casts
pH	Bilirubin	Bacteria
Specific gravity	Leukocyte esterase	Epithelial cells
Ketones	Nitrite	Crystals
Protein	WBC	Yeast

Other Laboratory Tests

Other laboratory tests will be performed at time points shown in [Table 1](#), [Table 2](#), and [Table 3](#) and are as follows: high sensitivity C-reactive protein (hs-CRP), TSH, FSH, hemoglobin A1c (HbA1c), sex hormones (luteinizing hormone, FSH, estradiol, and total testosterone), and pregnancy test (serum and urine).

Abnormal Laboratory Values and Laboratory Adverse Events

All laboratory values must be reviewed by the investigator or authorized designee.

Significantly, abnormal test results that occur after start of treatment must be repeated to confirm the nature and degree of the abnormality. When necessary, appropriate ancillary investigations should be initiated. If the abnormality fails to resolve or cannot be explained by events or conditions unrelated to the study medication or its administration, the Medical/Study Director must be consulted.

The clinical significance of an abnormal test value, within the context of the disease under study, must be determined by the investigator.

Criteria for reporting laboratory values as an AE are provided in [Section 9.4.5](#).

